10.2 Sample Size and Accrual

Power calculation based on the standard deviation in published reports (5) demonstrates that enrollment of 25 participants per arm is necessary to detect 1 standard deviation difference with 90% power. Further, published results from pilot studies in this population (7) and demonstrates that enrollment of 25 participants per arm is necessary to detect 0.5g/dL difference in hemoglobin with 90% power.

Prentice Women's Hospital of Northwestern Memorial performed over 100 abdominal myomectomies in 2013. Across a year-long study period, we anticipate identifying a minimum of 70 patients to evaluate our primary hypothesis. We have increased our sample size from 50 to 70 to account for the 9 participants that were either consented by a non-study team member, did not get the study drug due to an error at pharmacy or left the hospital after surgery thus we could not obtain a POD 1 which is needed for data analysis.

Following data collection from at least 20 participants in each arm, standard deviation calculations will be performed to confirm that the standard deviations in our sample population is similar. Power calculation will be repeated using the standard deviations in our active and placebo groups and additional participants will be enrolled as needed to achieve adequate power to evaluate our primary outcome of intraoperative blood loss.

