Objectives	Examine efficacy of buccal misoprostol at reduction in intraoperative blood loss at time of either an abdominal and laparoscopic myomectomy
Number of Subjects	70
Diagnosis and Main Inclusion Criteria	Symptomatic uterine fibroids, desire to retain uterus
Study Product(s), Dose, Route, Regimen	Misoprostol 400mcg buccally
Duration of administration	1 hour pre-procedure – At least 4 hours post-procedure
Reference therapy	Placebo (100mg Vitamin B6 tablets)
Statistical Methodology	Power calculation indicates 35 patients per arm will detect 1 standard deviation difference with 90% power. Fisher's exact test to be used for categorical variables and T test to be used for continuous variables with $P <.05$.

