10.0 STATISTICAL CONSIDERATIONS

10.1 Study Design/Study Endpoints

This is a double blinded randomized, controlled trial of women undergoing either an abdominal and laparoscopic myomectomy at a single university-affiliated tertiary care center. Women ages 18-50 years of age with clinically documented, sonographic evidence of uterine fibroids being scheduled for abdominal myomectomy were eligible for inclusion. Eligible participants will be randomized to receive preoperative 400cg buccal misoprostol or placebo on the basis of total fibroid volume, location (intramural or subserosal) and parity. Stratification by fibroid volume (or fibroid size) will be performed prior to randomization. Fibroid volume is defined as the cumulative volume of intramural and subserosal fibroids as measured on preoperative magnetic resonance imaging (MRI), or in the instance of patient contraindication to MRI, transvaginal ultrasound (TVUS). The data collection sheet (addendum) and chart of study variables below include definition of this variable and allow for ease of recording and tracking of this variable in our study database. Women with a history of gynecologic malignancy, critical anemia or blood dyscrasias and those with a history of prior myomectomies will be excluded.

List of Study Variables to be Collected:

Outcomes	Type	Definition
Estimated blood loss	Continuous	Intraoperative blood loss as estimated by intraoperative anesthesiologists and surgeons.
% drop in Hgb	Continuous	Ratio of the drop in hemoglobin over the starting hemoglobin ($Hg_{post-op} - Hg_{pre-op}$)/ Hg_{pre-op}
Duration of hospital stay (days)	Continuous	Number of days inpatient following abdominal myomectomy.
Duration of procedure (minutes)	Continuous	Number of days inpatient following abdominal myomectomy.
Post-op fever	Dichotomous	If patient has one Temperature >101.4 or two temperatures >100.4 , then yes. If not then no.
Adverse reaction to misoprostol	Dichotomous	If patient experiences vaginal bleeding, vomiting or diarrhea then yes. If not then no.

Exposures	Type	Definition
Pre-op Misoprostol	Dichotomous	If women randomized to receive misoprostol, then yes. If women randomized to placebo, then no.

Covariates	Type	Definition
Woman's Age	Continuous	Female age in years at time of abdominal myomectomy
Volume of fibroids (pre-op)	Continuous	Cumulative volume of intramural and subserosal fibroids based on preoperative imaging Will be used for stratification and randomization.

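### The interim sample-size re-check uses blood-loss SDs by arm, with no safeguard on who sees them, no target difference in mL and no maximum n

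*Combined protocol and SAP*

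**What the plan says.** Section 10.2 (Sample Size and Accrual) starts from a planning calculation: "Power calculation based on the standard deviation in published reports (5) demonstrates that enrollment of 25 participants per arm is necessary" to detect a one-SD difference with 90% power. Neither the SD nor the difference is given in mL. The only absolute difference in the section, 0.5 g/dL, is for hemoglobin. The Study Summary gives a larger number for the same target: "Power calculation indicates 35 patients per arm will detect 1 standard deviation difference with 90% power". Section 10.2 accounts for the increase: "We have increased our sample size from 50 to 70 to account for the 9 participants" who could not be used. It treats 70 as a minimum.

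The re-check comes next. "Following data collection from at least 20 participants in each arm", SDs are calculated to confirm that they are similar; the text does not say similar to what. Then: "Power calculation will be repeated using the standard deviations in our active and placebo groups and additional participants will be enrolled as needed", in order "to achieve adequate power to evaluate our primary outcome of intraoperative blood loss".

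The Study Summary and Section 10.1 describe the trial as double-blind. Section 10.1 defines the outcome: "Intraoperative blood loss as estimated by intraoperative anesthesiologists and surgeons". Section 7.6 provides for unblinding only on safety grounds. Section 11.3 (Data Management and Monitoring/Auditing) is marked not applicable. No independent statistician or committee is named.

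**The concern.** An SD for each arm can be computed only from data split by treatment. When surgeons and anesthesiologists estimate the outcome themselves, arm-level interim information should be kept from them and from the people who work with them. The plan contains no sentence that does this.

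The second gap is the anchor for the recalculation. A sample-size review based on variability needs a target difference fixed in the outcome's own units. One SD, with no mL value, leaves open whether the target is the planning SD or the SD just observed, and the two readings give very different answers. With no maximum either, the number to add would be settled after arm-level data exist.

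The re-check may well be needed. The trial now includes both abdominal and laparoscopic cases, so a published SD may not carry over.

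**Working it through.** **Inputs.** From the documents: a one-SD difference, 90% power, p < 0.05, 25 per arm (Section 10.2) or 35 per arm (Study Summary), and a look at 20 per arm. Assumed: two-sided test, equal allocation, unadjusted t-test, normal data, and ratios of true SD to planning SD of 1.25, 1.5 and 2. No document shows that the planning SD is wrong.

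**1. The plan's own figure.** n per arm = 2 × (1.960 + 1.2816)² × (SD/D)². With SD = D this is 21.01, so 22; the exact t-test needs 23. The planned 25 per arm gives 93.4% power, so the figure is sound. At 35 per arm, power for one SD is 98.5%.

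**2. Target read as the observed SD.** SD/D is then 1 by definition, so the answer is 22 (normal) or 23 (t-test) for any SD. The re-check could never add anyone.

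**3. Target fixed at the planning SD.** The look is at 20 per arm with a floor of 35. Power comes from simulation (60,000 runs per cell), except the last column, which is exact:

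| True SD / planning SD | n per arm for 90% | Arm-SD rule, cap 86 / 100 | Overall-SD rule, cap 86 / 100 | No re-check, 35 per arm |
|---|---|---|---|---|
| 1.25 | 34 | 92.9% / 93.1% | 92.2% / 92.1% | 91.0% |
| 1.5 | 49 | 89.8% / 90.1% | 87.4% / 87.6% | 78.5% |
| 2 | 86 | 87.2% / 88.3% | 86.0% / 87.0% | 54.1% |

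Type I error (cap 100) is 4.9-5.3% under both rules.

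**4. Why the maximum matters.** With a cap of 50 per arm and a ratio of 2, the arm-SD rule reaches only 69.9%. At the other end, 86 per arm is 172 participants, while the hospital "performed over 100 abdominal myomectomies in 2013" (laparoscopic volume is not given).

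**5. Overall SD without treatment codes.** If the true difference is D, the variance of 40 pooled values (20 and 20) exceeds the within-arm variance by (40/39) × D²/4 = 0.2564 D². Uncorrected, with SD = D, n would be 21.01 × 1.2564 = 26.4, so 27 instead of 22. Hence the correction of about D²/4. With normal data and a true difference of one SD, the corrected SD has a standard error of about 14% of the SD, against 11% for the within-arm pooled SD.

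If there is no effect, the correction takes off too much. At ratio 1.5 the expected variance becomes 2.25 − 0.2564 = 1.9936 (in units of D²), and 21.01 × 1.9936 = 41.9. With the floor of 35, n averages about 44-45 per arm, against 49 under the arm-SD rule.

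**6. What arm SDs could reveal.** For skewed blood loss (assumed lognormal, coefficient of variation 0.8 in both arms), a true mean ratio of 0.6 gives a median SD ratio of 0.60. Arm SDs can then hint at the effect. This depends on the assumed distribution.

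**The case against.** The strongest reply is that the existing rule performs well. Section 10.2 uses 90% power in planning and then says the calculation will be repeated, so carrying forward 90% and the same target is the ordinary reading. On that reading the arm-SD rule does slightly better than the overall-SD rule. This stands: the missing power level and trigger are matters of detail, and the 22-23 result needs the less natural reading.

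It is also fair to say that two group SDs disclose no participant's allocation, that the plan calls for no interim means, and that Section 7.6 gives no licence to unblind the team for a power check. This too stands, and it limits the blinding point to a missing safeguard.

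A reader might infer more than the documents support:

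- That the blind is broken. No text says the team will see the arm SDs.
- That type I error is inflated. It stays near 5% when only SDs drive n.
- That power falls to 79% or 54%. Those figures describe having no re-check at all, and the plan has one.
- That the published source for the SD is unusable. It cannot be checked from the documents; all that can be said is that its value in mL is not recorded.

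The reply leaves three gaps: who sees the arm-level data, what difference in mL the recalculation targets, and where it stops.

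**Conclusion.** The concern holds as a design weakness in how the re-check is specified. The plan splits the primary outcome by arm during a double-blind trial without restricting access, and it recalculates n with no recorded mL target and no maximum. The risk is to the blind and to the objectivity of the final n.

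The size is moderate. Read in the ordinary way, the rule delivers about 87-93% power at assumed SD ratios of 1.25-2 with caps of 86-100 per arm. Read literally against the observed SD, it can never raise n above 22-23 per arm. The gaps themselves do not depend on the assumed ratios, the normal distribution or the two-sided test; only the illustrative figures do.

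**What to change.** In Section 10.2, state the planning SD in mL and name it as the fixed target difference D. Then replace the re-check text with wording such as:

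*After about 40 participants have blood loss recorded, the overall SD will be computed without treatment codes, and its variance reduced by about D²/4. The sample size will be recalculated for fixed D at 90% power. It can only increase from 35 per arm and will not exceed [maximum]. The study team will see no arm-level means or SDs.*

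An equally acceptable alternative keeps the arm SDs, computed under masked labels or by a person outside the study team who returns only the new n. The fixed D, 90% power, increase-only rule and maximum apply in the same way. The sponsor should choose the maximum in advance; unadjusted, 49 per arm covers an SD 1.5 times planned and 86 covers twice. If the arm-level check has already been run, record who saw it.

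The cost is protocol wording, with no extra data. If the SD is as planned, the overall-SD rule averages 35.1 per arm. That version loses about 1-3 points of power for normal data and gives the smaller n shown above if there is no effect. It is also less precise for skewed blood loss: with no effect, its standard error is about 32% under the assumed lognormal, against about 13% for normal data (skewness makes arm-level SDs less precise too). Relative to the present rule, the masked-label version carries none of these costs.

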10.3 Data Analyses Plans

To determine whether women who take a pre-operative dose of misoprostol experience lower blood loss during abdominal myomectomy compared to matched controls who take placebo, we will perform linear regression. We will use this model to assess for the role of numerous covariates, including gravidity, parity and age. Secondary outcomes of percent hemoglobin drop, duration of procedure and length of inpatient hospitalization will be assessed using the T test and further evaluated with multivariate-adjusted linear regression where appropriate. The need for post-operative blood transfusion between groups will be assessed with the Chi-square (Fischer's exact) test. The role of numerous potential covariates will be assessed with Chi-square (Fischer's exact) test for dichotomous variables and T test for continuous variables with $p < 0.05$.

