1.5 Correlative Studies n/a**2.0 STUDY OBJECTIVES****2.1 Primary Objectives**

2.1.1 To determine the effect of 400mcg buccal misoprostol at least one hour pre-procedure on intraoperative blood loss at time of either an abdominal or laparoscopic myomectomy.

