2.3 Exploratory Objectives n/a**2.4 Endpoints**

Estimated blood loss as determined by anesthesia and surgeon at time of abdominal or laparoscopic myomectomy, difference between post-operative and pre-operative hemoglobin, post-operative temperature, and overall length of hospital admission.

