Mass of fibroids (post-op)	Continuous	Cumulative mass of intramural and subserosal fibroids based on pathology reports -Will be used to account for variability in final models.
Pre-treatment with Lupron, Depo-provera, OCPs	Dichotomous	Pre-operative treatment with Lupron, Depo-provera or OCP's
Intraoperative treatment with vasopressin or tourniquet	Dichotomous	Use of intraoperative vasopressin or tourniquet during myomectomy.

Other	Type	Definition	Use
Uterus size in weeks gestation	Ordinal	Uterus size in weeks gestation per pre-operative physical exam	Table 1 characteristic
History of Gynecologic Malignancy	Dichotomous	If history of gynecologic cancer (uterine, ovarian or cervical cancer), then yes. If not, then no.	Exclude if yes.
Uterine Anomaly	Dichotomous	If septate, unicornuate or bicornuate uterus, then yes. If abnormality is less severe than arcuate uterus or normal then no.	Exclude if yes.
Prior Cesarean Section Cycle	Dichotomous	If prior Cesarean delivery, then yes. If no prior Cesarean delivery, then no.	Table 1 characteristic, stratum-specific sub-analyses
Gravidity	Count	Number of prior pregnancies	Table 1 population characteristic
Gravid	Dichotomous	If number of pregnancies is 1+, then yes If number of pregnancies is 0, then no	Table 1 characteristic, stratum-specific sub-analyses
Parity	Count	Number of prior pregnancies	Table 1 population characteristic
Living children	Count	Number of living children	Table 1 characteristic
Woman's Age (SART categories)	Categorical	Group by age in years at abdominal myomectomy: <30 30-34 35-37 38-39 40-42 43+	Table 1 population characteristic
Race	Categorical	Group by race: White, Black/Africa-American, Hispanic, Asian/Pacific	Table 1 population characteristic

		Islander, American Indian/Alaskan Native, Middle-Eastern	
--	--	--	--

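### Planned surgical route is not pre-specified as a covariate although the trial covers abdominal and laparoscopic myomectomy: a cheap, low-severity improvement whose gain depends on unknowns

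*Combined protocol and SAP*

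**What the plan says.** Both routes are intended. Objective 2.1.1 concerns "intraoperative blood loss at time of either an abdominal or laparoscopic myomectomy", the endpoint in 2.4 is "Estimated blood loss as determined by anesthesia and surgeon at time of abdominal or laparoscopic myomectomy", and 10.1 opens by describing a trial of "women undergoing either an abdominal and laparoscopic myomectomy at a single university-affiliated tertiary care center". Section 1.2 refers to laparoscopic surgery being added to the study.

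The statistical section did not fully follow. The next sentence of 10.1 describes women "being scheduled for abdominal myomectomy were eligible for inclusion". Section 10.3 frames the primary question as whether women given misoprostol "experience lower blood loss during abdominal myomectomy compared to matched controls who take placebo, we will perform linear regression". Inclusion criterion 3.1.1 is a two-route phrase with the second route's word missing.

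On design variables, 10.1 randomises "on the basis of total fibroid volume, location (intramural or subserosal) and parity", with stratification by fibroid volume. Its covariate table lists:
- age;
- pre-operative fibroid volume;
- post-operative fibroid mass, defined as "Cumulative mass of intramural and subserosal fibroids based on pathology reports -Will be used to account for variability in final models";
- hormonal pre-treatment;
- an item for vasopressin or tourniquet, defined as "Use of intraoperative vasopressin or tourniquet during myomectomy".

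Surgical route appears in none of the tables. Section 10.3 names gravidity, parity and age as examples of covariates, not as a closed list. Section 10.2 plans an SD check once each arm has at least 20 participants, with more enrolment if the repeated power calculation calls for it.

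**The concern.** Adding laparoscopic cases introduced a new source of variation, and nothing in 10.1 to 10.3 deals with it by name. If mean blood loss differs between routes, three things follow.

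- An analysis without route carries the between-route variance in its error term.
- A chance difference in route mix between the arms moves the estimate.
- An SD taken without route at the 10.2 check includes variance that one model term would remove.

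Planned route is known before dosing, so it is a clean baseline covariate. Fibroid mass and vasopressin or tourniquet use are recorded after dosing. Because the covariate list is open, route could be added later, but a choice made after seeing the data carries less weight than one fixed in advance.

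**Working it through.** **Inputs from the documents.** The effect is 1 SD with 90% power and 25 per arm (10.2). The Study Summary gives 35 per arm, 70 in total. The 70 allows for 9 unusable participants (10.2), and 70 − 9 = 61, or about 30 per arm. The significance level is 0.05; sidedness is not stated, so two-sided is assumed.

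**Assumed inputs, because the documents do not give them.** These are the laparoscopic share p and the route difference in mean blood loss D, in within-route SDs. Within-route SDs are taken as equal.

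**The plan's own figure.** An exact two-sample t-test for a 1 SD difference at 90% power needs 23 per arm, close to the stated 25. Power is 93.4% at 25 per arm, 96.8% at 30 and 98.5% at 35.

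**Precision.** Leaving route out multiplies the SD by √(1 + p(1−p)D²). Adjusting removes that factor but costs about √((N−3)/(N−4)) for the extra degree of freedom and chance imbalance. With N = 70 the cost is √(67/66) = 1.0075. The ratio of adjusted to unadjusted SE is therefore 1.0075 / √(1 + p(1−p)D²), if no other covariate absorbs route:

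| D (SD) | p = 0.1 | p = 0.5 |
|---|---|---|
| 0 | +0.8% | +0.8% |
| 0.25 | 1.0075/√1.0056: +0.5% | 1.0075/√1.0156: about 0% |
| 0.5 | 1.0075/√1.0225: −0.4% | 1.0075/√1.0625: −2.3% |
| 1 | 1.0075/√1.09: −3.5% | 1.0075/√1.25: −9.9% |

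A simulation at N = 70, p = 0.3 and D = 1 gave SEs of 0.261 without route and 0.239 with it, about 8% lower. The formula gives 8.4%.

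**Power for a 1 SD effect without route.** If the plan's 1 SD is a within-route SD, the standardised effect becomes 1/√(1 + p(1−p)D²). The noncentrality is that value times √(n/2), on 2n − 2 degrees of freedom. At 35 per arm:

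| D (SD) | Half laparoscopic | 20% laparoscopic |
|---|---|---|
| 0.5 | 97.9% | 98.1% |
| 1 | 95.8% | 96.9% |
| 2 | 83.0% | 89.6% |

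The route difference at which power falls to 90% is:

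| Per arm | Half laparoscopic | 20% laparoscopic |
|---|---|---|
| 35 | 1.57 SD | 1.97 SD |
| 30 | 1.23 SD | 1.54 SD |

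If other covariates absorb half the route variance, each threshold is multiplied by √2: 2.22 and 2.78 SD at 35 per arm, 1.74 and 2.18 SD at 30. If the plan's 1 SD is a total SD, route variance is already inside it and there is no shortfall.

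**The 10.2 re-estimate.** Using an SD that still contains route, 90% power needs 24, 28 or 44 per arm for D = 0.5, 1 or 2 (half laparoscopic), or 23, 26 or 36 (20%). With route removed it needs 23.

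**Chance imbalance.** Treating the arms as independent binomials of 35, a gap of 5 or more laparoscopic cases has probability 28% (half laparoscopic) or 18% (20%). These figures ignore any balance gained through volume stratification. A gap of 5 shifts the unadjusted estimate by 5/35 = 0.14 SD for each 1 SD of route difference.

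**The case against.** The strongest reply is that no gain can be shown from the documents. The laparoscopic share and blood loss by route are both absent (the only case count, in 10.2, is for abdominal cases), and at a 0.25 SD route difference adjusting gains nothing. This stands, and the benefit has to be stated as conditional.

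Second, other listed variables may already do part of the work. Pre-operative fibroid volume is both a stratifier and a listed baseline covariate, and fibroid mass and vasopressin or tourniquet use may also track route. This stands too. The documents do not show how closely any of them tracks route, so the figures with no absorption are the upper end.

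Third, the 10.3 list is open and the data collection sheet is attached but not shown. Route is unnamed rather than excluded, and may well be recorded.

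A reader might also infer more than the documents support:
- *The treatment estimate is biased.* Randomisation rules out systematic bias from route.
- *The trial is underpowered.* That needs a large route difference and a within-route reading of the 1 SD. Section 10.2 takes its SD from a published report without saying which kind it is.
- *Laparoscopic cases fall outside the primary analysis.* The abdominal-only wording in 10.1 and 10.3 reads as a leftover, given 2.1.1, 2.4 and the first sentence of 10.1.

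What survives is that a baseline feature the trial deliberately broadened is not fixed in advance in the primary model.

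**Conclusion.** The point holds as a low-severity improvement and does not threaten the trial's conclusion. The textual gap is clear. Its size rests on an assumed laparoscopic share, an assumed route difference, equal within-route SDs and no absorption by other covariates. On those terms the benefit runs from nil at about 0.25 SD to an SE nearly 10% smaller at 1 SD with an even route mix. Unadjusted power for the planned effect stays above 90% up to route differences of about 1.6 SD (half laparoscopic) or 2.0 SD (20%) at 35 per arm, and about 1.2 or 1.5 SD at about 30 per arm. The case for acting is that the cost is very small and known, while the possible gain is moderate.

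**What to change.** - Add planned route (abdominal or laparoscopic, as booked before dosing) to the 10.1 variable list. Use planned rather than actual route, since actual route can change during surgery.
- Before the 10.2 SD check and before unblinding, name it in 10.3 as a fixed covariate in the primary blood-loss regression.
- Use the residual SD from that model in the 10.2 re-estimate.
- Align 3.1.1 (missing word), 10.1 and 10.3 with objective 2.1.1.

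The cost is one field known before dosing, one degree of freedom and some wording. If route turns out not to matter, the interval is about 0.8% wider and power at 35 per arm for a 1 SD effect moves from 98.5% to about 98.3%. No new randomisation stratum and no added enrolment are needed.

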5.0 STUDY PROCEDURES

5.1 Screening/Baseline Procedures

Assessments performed exclusively to determine eligibility for this study will be done only after obtaining informed consent. Assessments performed for clinical indications (not exclusively to determine study eligibility) may be used for baseline values even if the studies were done before informed consent was obtained.

All screening procedures must be performed within ninety days of registration unless otherwise stated. The screening procedures include:

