5.1.8 Baseline Hemoglobin

Baseline serum hemoglobin will be determined for all patients.

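### Section 10.3 names an unadjusted t test on percent hemoglobin drop, leaves adjusted regression optional, and nowhere pre-specifies pre-operative hemoglobin as a covariate: a modest loss of precision and consistency

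*Combined protocol and SAP*

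**What the plan says.** Section 10.3 lists hemoglobin among the secondary outcomes: "Secondary outcomes of percent hemoglobin drop, duration of procedure and length of inpatient hospitalization will be assessed using the T test". The same sentence continues that these outcomes will be "further evaluated with multivariate-adjusted linear regression where appropriate". It gives no criterion for when that applies and no covariates for the hemoglobin model.

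The variable table in 10.1 defines the outcome as "Ratio of the drop in hemoglobin over the starting hemoglobin", that is (post − pre)/pre. Section 2.4 lists a different quantity, "difference between post-operative and pre-operative hemoglobin", with no division. The hemoglobin power statement in 10.2 is in absolute units: 0.5 g/dL, 90% power, 25 per arm.

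On availability, 5.1.8 says "Baseline serum hemoglobin will be determined for all patients". On adjustment, the only covariates named in 10.3 belong to the blood-loss model: "We will use this model to assess for the role of numerous covariates, including gravidity, parity and age". The covariate rows of 10.1 are age, fibroid volume, fibroid mass, hormonal pre-treatment, and vasopressin or tourniquet use. Fibroid mass carries the note "Will be used to account for variability in final models". Pre-operative hemoglobin is in neither list.

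**The concern.** Pre-operative hemoglobin is an obvious candidate to predict post-operative hemoglobin, and it is already collected. Dividing the change by baseline is not the same as adjusting for it. It fixes the weight given to baseline in advance, whereas regression estimates that weight from the data. Where the fixed weight is wrong, the arm comparison carries avoidable noise, including any chance baseline difference between the arms.

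Hemoglobin is the laboratory-measured counterpart to a blood loss that anesthesiologists and surgeons estimate, so its precision has some value. An adjusted model that is optional and unspecified also leaves open, until the data are seen, which hemoglobin result will be the main one. Finally, the endpoint list, the variable definition and the power statement do not share one scale.

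**Working it through.** **Inputs from the documents:** 35 per arm (Study Summary); difference 0.5 g/dL, 90% power, 25 per arm (10.2); significance level 0.05 (Study Summary, 10.3), taken as two-sided. **Assumed, because not given:** pre-operative mean 12 g/dL, equal pre and post SD of 1.0 to 1.5 g/dL, mean drop 1 to 3 g/dL, and the pre-post correlation ρ.

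**1. The plan's own figure.** The 25 per arm for 0.5 g/dL cannot be reproduced, because no hemoglobin SD is stated. Working backwards, a t test with 25 per arm and 90% power detects 0.936 SD, so the implied SD is 0.5/0.936 = 0.534 g/dL. The normal approximation gives 0.5/[(1.960 + 1.282) × √(2/25)] = 0.545 g/dL.

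**2. Formula for the gain.** Let k = 1 − (mean drop/pre-operative mean). To first order, the variance of the adjusted comparison relative to the percent-drop t test is (1 − ρ²)/(1 + k² − 2kρ). Since 1 + k² − 2kρ = (1 − ρ²) + (k − ρ)², the effective sample-size ratio is

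1 + (k − ρ)²/(1 − ρ²).

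The percent-drop test loses nothing when ρ = k, and loses precision on either side of that value.

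**3. Numbers.** A mean drop of 1 g/dL gives k = 11/12 = 0.917; a drop of 3 g/dL gives k = 9/12 = 0.75.

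| ρ | Formula, drop 1 g/dL | Formula, drop 3 g/dL | Simulated gain, SD 1.0 to 1.5, drop 1 to 3 g/dL |
|---|---|---|---|
| 0.4 | 1 + 0.267/0.84 = 1.32 | 1 + 0.1225/0.84 = 1.15 | about 16% to 41% |
| 0.5 | 1 + 0.174/0.75 = 1.23 | 1 + 0.0625/0.75 = 1.08 | about 9% to 29% |
| 0.7 | 1 + 0.047/0.51 = 1.09 | 1 + 0.0025/0.51 = 1.00 | about 0% to 13% |
| 0.8 | 1 + 0.0136/0.36 = 1.04 | 1 + 0.0025/0.36 = 1.01 | about 0% to 5% |

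The simulated upper ends exceed the formula, which is a first-order approximation. At high correlation with a large drop the gain returns: for ρ = 0.93 and a 3 g/dL drop the formula gives 1 + 0.0324/0.1351 = 1.24, and simulation at SD 1.5 gives 1.22. No setting showed a material loss from adjusting.

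**4. In terms of power.** With 35 per arm, a true difference of 0.5 g/dL, SD 1.0 and mean drop 1.5 g/dL, simulated power for the percent-drop t test versus the adjusted regression is 51% vs 62% (ρ = 0.4), 58% vs 66% (0.5), 67% vs 73% (0.6) and 92.6% vs 93.0% (0.8).

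**5. Chance imbalance.** With SD 1.0, ρ = 0.5 and a 1.5 g/dL drop, k = 0.875. Each 1 g/dL of baseline difference between arms then shifts the comparison by the equivalent of k − ρ = 0.375 g/dL. The SD of the baseline difference is 1.0 × √(2/35) = 0.24 g/dL, so a typical shift is 0.24 × 0.375 = 0.09 g/dL, against a target of 0.5.

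**6. Where ρ might lie.** If the 0.534 g/dL is the SD of the pre-post change, which 10.2 does not say, then ρ = 1 − 0.534²/(2 × SD²). That is 1 − 0.285/2 = 0.86 at SD 1.0 and 1 − 0.285/4.5 = 0.94 at SD 1.5. Pulling the other way, "All screening procedures must be performed within ninety days of registration unless otherwise stated" allows an old baseline value, which could lower ρ.

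**The case against.** The strongest reply is that the plan already provides for adjustment. A reader who stops at the t test might infer that hemoglobin is never adjusted. The rest of the sentence rules that out: multivariate regression is foreseen, and nothing in it excludes pre-operative hemoglobin. The covariates named in 10.3 are introduced as examples and belong to the blood-loss model. This reply stands, but it does not settle the matter. The regression is conditional, comes after the t test, and has no stated covariates, so nothing commits the analysis to using baseline hemoglobin.

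A second reply is that the gain may be negligible. If the SD implied by 10.2 is a change SD, the correlation would be about 0.86 to 0.94, where adjustment usually adds little. This also stands as a possibility. It rests on an inference about an SD that the plan does not state.

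Two further readings are tempting. One is that women who start high generally show larger percent drops. The sign depends on whether ρ is below or above k: in simulation the correlation of percent change with baseline was −0.19 at ρ = 0.8 with a 1 g/dL drop, +0.03 at 0.85 with 2 g/dL, and +0.15 at 0.9 with 2 g/dL. The documents do not show which case applies. The other is that leaving out the baseline biases the comparison. Under randomization the percent-drop t test remains valid, and chance imbalance costs precision only.

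**Conclusion.** The point holds as a modest matter of precision and consistency on a secondary outcome. The named analysis is an unadjusted t test on percent drop, adjustment is optional and unspecified, and baseline hemoglobin is not pre-specified although it is planned for all participants. The analysed scale also differs from the endpoint in 2.4 and the effect size in 10.2.

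The size cannot be fixed from the documents. Under the assumptions above, the gain is material at correlations of 0.4 to 0.5, small at 0.7 and about nil at 0.8. Beyond that it rises again only if the mean drop is large. The primary outcome, intraoperative blood loss, is already assigned to linear regression and is not affected. The change is worth making because it costs almost nothing and showed no material loss in any setting tried; the trial's main conclusion does not depend on it.

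**What to change.** In 10.3, name as the main hemoglobin analysis a linear regression of post-operative hemoglobin (g/dL) on arm and pre-operative hemoglobin. Add the stratification factor if the primary model includes it. Report the adjusted difference between arms in g/dL with its 95% confidence interval. Keep percent drop as a descriptive summary, and align the outcome row in 10.1 with 2.4 and with the g/dL scale of 10.2. Add pre-operative hemoglobin to the covariate rows of 10.1, and drop the conditional wording on adjustment for this outcome.

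The cost is a few lines of analysis text. Both hemoglobin values are already needed to compute the planned percent drop, so no new data, visits or participants are required.
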